Our main hypothesis is that we can reduce all-cause mortality to 11.2% by measuring suPAR on admitted patients. Using a 5 % level of significance and a power of 80 %, we will need a sample of 7340 patients in each randomization group to detect this difference an absolute risk reduction in mortality at least 10 months after admission of 1.5 %.

Based upon numbers from the two emergency departments, approximately 170 patients are admitted on a daily basis. During the inclusion period it will be possible to collect data on 10,700 patients in both active- and control periods. This will be sufficient to assess the primary hypothesis.

Ethics and approvals

The study was approved by the board of directors at each participating hospital and department heads of the emergency departments gave consent. The study was presented to the Regional Ethics Committee, who decided that no formal approval was needed in accordance with Danish law (Jr. Nr.: FSP-15003590). All processing of personal data followed national guidelines in accordance with Danish law and the study was approved by the Danish Data Protection Agency (HGH-2015-042, I-Suite nr.04087) and will be registered at the Danish Patient Safety Authority. The study is registered at clinicaltrials.org (NCT02643459).

Economy

Expenses related to the study are financed by ViroGates A / S. Together with ViroGates external funding will be sought for parts of or the entire project.

References

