The study was presented to the Regional Ethics Committee, who decided that no formal approval was needed in accordance with Danish law. The study has been approved by the Danish Patient Safety Authority (3-3013-1744/1) and data management has been approved by the Danish Data Protection Agency (ID: HGH-2015-042, I-suite: 04087).

Study variables and endpoints:

The following data are collected for the included patients:

- Age
- Results of the routine blood tests at the index admission including suPAR where available. Routine biomarkers: Hemoglobin, Leukocytes, thrombocytes, sodium, potassium, C-reactive protein, Creatinine, ALAT, Albumin, Calcium, lactate. suPAR in intervention periods
- Gender
- Personal Identification number (Danish Civil Registration number (CPR))
- At follow-up (10 months after inclusion of last patient) the following data is collected from the National Patient Registry (NPR)
- Contacts with the hospital system (including all historical contacts)
- Information regarding admissions (date, time and place of admission and discharge)

- Diagnoses (follow-up during study period, historical and in relation to index admission)
- Date of death or immigration (only very few immigrations are expected)
- Charlson score will be calculated using registered diagnoses in NPR dating two years back from index admission

Sample size calculation

In a previous unpublished study of patients acutely admitted to an Emergency Department in Denmark 12-month mortality was 12.7% and readmission rate was 16% within 5 months. Using a 5% level of significance and a power of 80%, the study will need to include 7,340 patients in each group to detect an absolute risk reduction in mortality of 1.5% at 10 months after admission. The two participating hospitals approximately admit 170 patients on a daily basis. During the study period approximately 10,700 patients will be included in every group.

Study end

The follow-up for all patients ends at April 6 2017 and this date will be used as the censoring time for the main analysis.

Statistical plan for main outcome paper

Statistical analyses will be performed using SAS and R.

Consort diagram:

A modified CONSORT trail profile will be used to describe patient flow and total number patients in each group. All patients not included in analysis will be explained.

Baseline description of groups:

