A secondary analysis will be performed where the observational period ends if a patient is readmitted within the inclusion period. We anticipate, that the patients in the secondary analysis will seem healthier and the possible effect of the intervention weaker, although showing the same trend as the main analysis. Notable difference between the results of the main and the secondary analysis strategies will be considered critically.

Finally a per protocol weighted analysis is planned. In this analysis, only patients with a suPAR measurement are included in the intervention group. In order to investigate the difference between these results and the main analysis, we will analyze the mortality differences between patients with and without a suPAR measurement in the intervention periods.

Kaplan-Meier plots will be used to illustrate survival. Robust standard errors will be employed to account for the clustering. $P < 0.05$ will be considered statistically significant

Adjusted analyses of primary endpoint:

Three additional models will also be examined to further examine any role of differences in baseline values of the two groups. The first will include age, sex, CRP and center. The second will further include Charlson score. The third will include all variables used in the descriptive statistics. Results will be presented as hazard ratios with 95% confidence intervals. A forest plot will illustrate the results.

Sensitivity analyses of the primary endpoint:

Sensitivity analyses will be performed: One analysis where all readmissions are censored and a second analysis with only 10 months follow-up for all patients.

Secondary endpoints:

The predefined secondary endpoints of the study are: all-cause mortality at one month of admission; short admission (<24 h) to the emergency department; admission to the medical wards; admission to the intensive care unit; new (not previously registered) cancer diagnosis at the end of the study; length of stay during admission; readmission at one and three months; and economical expenses.

All-cause mortality at one month will be analyzed similar to the primary outcome. The discriminative ability of suPAR with regard to mortality at one and ten months will be assessed by using area under the curve for receiver operating characteristics curves as well as sensitivity, specificity, negative- and positive predictive value. To compare

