readmission risk, we will use Cox regression analysis. Cumulative incidence rates adjusted for competing risk (death, readmission) will be estimated. Unpaired t-test will be used to compare length of stay between groups.

Subgroup analyses:

Primary and secondary endpoints (mortality, readmissions, length of stay, discharge from the ED) will be analyzed in the following subgroups according to primary diagnosis at admission: cardiovascular disease, cancer, infections, neurological disease, surgery done during current admission, and patients aged 65 years or older. When Triage data is available, outcomes will be assessed according to DEPT triage categories, as suPAR previously has shown strongest prognostic effect in patients with lowest DEPT triage. All-cause mortality will be analyzed similar to the primary endpoint.

Handling of missing data:

The primary outcome analysis should be subject to no or little missing data as it is based on Danish register data.

Handling of diagnoses for outcome and subgroups:

Diagnoses obtained from the National Patient Registry are coded with the ICD-10 system. The original chapters will be used to group patients according to diagnoses. The primary diagnosis will be used when constructing subgroups and both primary and secondary diagnoses will be used to calculate Charlson score. The following will define the subgroups:

Cancer: Chapter II: Neoplasms (C00-C97 + D37-D48).

Cardiovascular disease: Chapter IX: Diseases of the circulatory system (I09-I52 + I70-I89)

Infections: Chapter I: (A00-B99 + J00-J22 + N10-N11+ N30-N31 + G00-G09)

Neurological disease: Chapter VI: Diseases of the nervous system (G09-G47 + I60-I69)

Surgical conditions: Presence of surgical procedure codes divided into different specialties (general, orthopedic, other)

Summary of changes to the protocol

Changes to the protocol were made before outcome data was available. The final protocol was published as a design article on August 5 2016:

<https://www.ncbi.nlm.nih.gov/pubmed/27491822>

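### The subgroup analyses have no interaction test, complement group or rule for interpretation, so an effect equal in everyone would usually look uneven across subgroups

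*Combined protocol and SAP*

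**What the plan says.** Under Subgroup analyses, the final SAP states: "Primary and secondary endpoints (mortality, readmissions, length of stay, discharge from the ED) will be analyzed in the following subgroups". The subgroups are cardiovascular disease, cancer, infections, neurological disease, surgery during the admission, and age 65 or over. Mortality is to be analysed in the same way as the primary endpoint, which means the weighted Cox comparison of intervention with control set out under Primary outcome analysis.

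Where triage data exist, outcomes are also to be examined by DEPT category, "as suPAR previously has shown strongest prognostic effect in patients with lowest DEPT triage".

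The only significance rule in the final SAP closes the Primary outcome analysis section: P below 0.05 "will be considered statistically significant". It is not repeated in the subgroup section.

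No interaction or heterogeneity test, complement group, multiplicity control, exploratory label or interpretation rule for subgroups appears in the final SAP, the Original Statistical analysis plan or the protocols. The forest plot in the final SAP belongs to the covariate-adjusted models of the primary endpoint, not to the subgroups.

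**The concern.** A subgroup analysis is normally read as an answer to one question: does the effect differ between kinds of patient? Repeating the main comparison inside each subgroup answers another: is there a detectable effect among these patients? That depends as much on the number of deaths in the subgroup as on the effect. A large subgroup can pass 0.05 and a small one miss it when the effect is identical in both.

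The listed subgroups are likely to differ widely in size, and the only age group named has no counterpart below 65. A reader of the results would therefore have significant and non-significant subgroups side by side, with nothing to show whether they differ by more than chance. At stake are statements that suPAR reporting helps one kind of patient and not another, which could steer where the test is introduced.

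**Working it through.** **Inputs.** From the final SAP, Sample size calculation: "12-month mortality was 12.7% and readmission rate was 16% within 5 months". The same section sets a target of 7,340 per arm for an absolute reduction of 1.5 percentage points, at 80% power and 5% significance, and expects about 10,700 per arm. From the final protocol, Power calculation: mortality reduced to 11.2%. Allocation is 1:1 (final SAP, Design). The documents do not give subgroup shares, so these are assumed and varied.

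**The plan's own figure.** With p1 = 0.127, p2 = 0.112 and mean 0.1195, two-sided 5%, pooled variance under the null:

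n = [1.960·√(2·0.1195·0.8805) + 0.8416·√(0.127·0.873 + 0.112·0.888)]² / 0.015² = (0.8991 + 0.3860)² / 0.000225 = 7,340 per group. The stated size is reproduced exactly.

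**Overall power at 10,700 per arm.** SE = √[(0.127·0.873 + 0.112·0.888)/10,700] = 0.00443. z = 0.015/0.00443 = 3.38. Power = Φ(3.38 − 1.96) = 92.3%. At 7,340 it is 80.0%.

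**Power within a subgroup, same effect in everyone.** A subgroup holding share s of patients has expected z = 3.38·√s at 10,700. For s = 0.10, z = 1.07 and power = Φ(−0.89) = 18.7%.

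| Share of patients (assumed) | 7,340 per arm | 10,700 per arm |
|---|---|---|
| 5% | 9.1% | 11.4% |
| 10% | 14.1% | 18.7% |
| 20% | 24.0% | 32.7% |
| 30% | 33.5% | 45.7% |
| 50% | 50.8% | 66.7% |

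**Six subgroups together.** Risk differs between subgroups, and information follows deaths, so this step uses shares of deaths.

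- Hazard ratio = ln(1 − 0.112)/ln(1 − 0.127) = 0.875, the same in everyone.
- Expected deaths = 2·10,700·0.1195 = 2,557, or 2·7,340·0.1195 = 1,754.
- Each log hazard ratio is drawn as normal with variance 4/deaths; 200,000 simulated trials per scenario.
- Four sets of shares: the five diagnosis or surgery groups hold 5%, 10% or 18% of deaths each, or 10, 20, 25, 5 and 10%. They are treated as disjoint.
- Age 65 or over holds 80% of deaths in the first three sets and 70% in the fourth, and overlaps the other groups.
- A subgroup counts as significant if z is below −1.96, that is, in favour of the intervention.

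| Result across the four sets | 7,340 per arm | 10,700 per arm |
|---|---|---|
| Power, each diagnosis or surgery group | 9-29% | 11-40% |
| Power, age 65 or over | 65-71% | 81-86% |
| One to five of six significant | 78-83% | 90-93% |
| The same, given a significant overall result | 90-94% | 94-97% |
| None significant | 17-22% | 7-10% |
| All six significant | at most 0.05% | at most 0.2% |

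Much of the mixed picture comes from the age group passing while most of the smaller groups fail.

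**What an interaction test would do.** In the same simulations, testing each subgroup against its complement flags a false difference in 4.9-5.1% of trials per factor. Across six unadjusted tests at least one is flagged in 25-27%; for independent tests, 1 − 0.95⁶ = 26.5%.

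**The case against.** The strongest reply is that the SAP is brief rather than wrong. It nowhere prescribes separate tests at 0.05 within each subgroup, and the subgroups were few, named, mostly defined by ICD-10 codes and fixed before outcome data were available. All of that stands. That P<0.05 governs the subgroups is an inference: it is the SAP's only threshold, and subgroup mortality follows the primary method. But no method for comparing subgroups is given, so an analyst following the text would produce only within-subgroup results.

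A reader might infer from the triage sentence that the SAP hypothesises a larger intervention effect in the lowest category. The text does not support this. It speaks of prognostic strength, which is how well the marker predicts; that is a reason to look, not a stated hypothesis about treatment effect. Nor is a complement missing there, since the categories cover all triaged patients.

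The figures also assume that the full design effect is true. With no effect, six independent tests would give at least one P<0.05 in 26.5% of trials. The shares are assumed too. The only guide is the pocket-card table in the original protocol (Figure 1), from acute medical patients at another hospital with a cut at 70 years: the older 1,691/4,343 = 39% had 309/386 = 80% of 90-day deaths. This is why the six-subgroup step uses deaths rather than patients.

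Finally, surgery during the admission happens after allocation and might itself be affected by the intervention. An interaction test does not cure that.

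**Conclusion.** The concern holds in this form: the final SAP has no interaction test, no complement group and no rule for interpreting subgroup results. If the effect were the design effect and equal in everyone, the six subgroups would give a mixed picture on mortality in about 78-93% of trials, and that picture could be misread as a differential effect. The range rests on independent patients, 7,340 to 10,700 per arm, assumed shares, and disjoint diagnosis and surgery groups. Clustering and weighting are ignored; where they inflate the variance, within-subgroup power is lower still.

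Three stronger readings are not supported:

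- **Subgroup against complement.** At 10,700 per arm with a uniform effect, exactly one of a subgroup and its complement is significant in 44% of trials (50/50 split), 62% (20/80) or 75% (10/90). The SAP does not plan complement tests, so these figures do not describe it. With no effect the figure is 2·0.05·0.95 = 9.5%.
- **Six subgroups by four endpoints.** One might quote 1 − 0.95²⁴ = 71% for at least one false positive under no effect. That is an upper figure for independent tests. It is a multiplicity problem, which interaction tests alone would not remove.
- **The trial's main result.** Nothing here bears on the primary analysis. The consequence is confined to what may be said about subgroups.

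**What to change.** For each subgroup factor, fit one model in all patients with arm, factor and arm-by-factor terms, on the scale of the endpoint:

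- mortality and readmission (Cox): ratio of hazard ratios, with the planned weights and robust standard errors where the main analysis of that endpoint uses them;
- length of stay, now planned as a t-test: difference between the mean differences;
- discharge from the ED, for which no model is named: interaction as a ratio of odds ratios or of risk ratios, chosen in advance.

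For DEPT triage, put all categories in one model. Report each interaction estimate with its 95% CI and P value, and show each subgroup beside its complement. Label the tests exploratory, since six unadjusted tests still carry about a 26% chance of at least one P<0.05. State that no claim of differential effect will rest on a within-subgroup P value.

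This needs a short paragraph in the SAP, a named model for ED discharge and some extra models, but no new data. The real cost is low power. With share f of deaths in the subgroup, the variance of the interaction is that of the overall log hazard ratio times 1/[f(1 − f)]. The standard error is therefore 2 times the overall one for a 50/50 split, 2.5 times for 20/80 and 3.3 times for 10/90. Fewer subgroup claims could be made.
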